##### 1. Objective adverse events

1. Objective adverse events will be described based on objective findings found during reassessment immediately following the initial ketorolac administration, and at the 30 minute and 60 minute re-evaluation intervals. Objective adverse events are any (1.) subjective events (signs or symptoms) which can be validated or observed by study investigators (such as rash or obvious dyspnea), (2.) are obvious to the investigator, but perhaps not the patient (mild facial swelling or rash) or (3.) abnormal vital signs. Blood pressure and heart rate measurements will be taken at the 30 minute and 60 minute intervals. Any deviation of blood pressure or heart rate which would meet exclusion criteria for this study would prompt immediate notification of the attending provider and the patient would be excluded from the study.

##### 2. Subjective adverse events

1. Subjective adverse events are any symptoms conveyed by the subject, but are not measureable, observable or verifiable by the investigator. To better facilitate analysis, a list of the most common subjective adverse events, according to UpToDate.com, will be provided to the study subject to choose from. Examples of subjective adverse events may include dizziness, light headedness or nausea (this is not an exhaustive list of subjective

adverse events). Study investigators will review, confer, agree upon and categorize the adverse events (based on the subjective report) prior to submitting them to the statistician for analysis.

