#### 9.4 Study Design:

Describe study design in one to two sentences (e.g., prospective, use of existing records/data /specimens, observational, cross-sectional, interventional, randomized, placebo-controlled, cohort, etc.). Specify the phase – Phase I, II, III, or IV – for FDA-regulated investigational drug research

This study utilizes a single-blinded, randomized controlled non-inferiority trial design.

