#### 9.6 Benefit to the DoD:

State how this study will impact or be of benefit to the Department of Defense

It is the primary aim of the study to demonstrate that low dose intramuscular ketorolac, 15 mg, is not inferior to high dose intramuscular ketorolac, 60 mg, for the treatment of musculoskeletal pain. In proving the primary aim of the study, it is our hypothesis that the total man hours lost will decrease as a result of better pain management at the time of presentation to the emergency department. Second, by demonstrating that the lower dose is not inferior, this study may help increase patient satisfaction scores within military emergency departments. Lastly, by providing evidence with this single-blind, non-inferior study, it may be inferred that our results will add to the current set of literature which could become a pathway to building a larger multi-center study.

During his tenure, the previous Chief of Staff for the Army, GEN Mark Miley, clearly maintained that readiness is the priority of the U.S. Army. The military medical community is front and center in maintaining the DoDs level of readiness. This study aims to demonstrate that low dose intramuscular ketorolac is not inferior to high dose intramuscular ketorolac. By demonstrating non-inferiority, it is postulated that patients receiving the lower dose of ketorolac may experience a faster return to work period. This shorter period may equate to less man hours lost. This hypothesis is based on previously demonstrated higher incidents of dose related adverse events.

We anticipate that there will be a lower rate of adverse outcomes by utilizing lower doses of ketorolac. These findings result in multiple benefits to the DoD, service member, and beneficiary. First, by showing a lower rate of adverse outcomes, treating with the lower dose may improve readiness by decreasing lost man hours. Secondly, reducing the amount of adverse effects while maintaining the same level of therapy, patient satisfaction may improve, as well.

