#### Randomization and Study Subject Packet Creation

Fully enrolled subjects will be randomized based on a two block randomization generated by the website [www.graphpad.com](http://www.graphpad.com). Randomization will be created so there are two groups (two block randomization), one which will receive 15 mg of intramuscular ketorolac and one which will receive 60 mg of intramuscular ketorolac. Each group (block) will consist of 61 subjects per the power analysis described later in this document and will be assigned a Subject Study Number.

The Subject Study Number will be comprised of a "K" for ketorolac, "15" or "60" designating which dose of ketorolac will be administered and then a specific number reflecting their position within the randomization block (randomization block number). For instance, a Subject Study Number of "K15-30" would signify that this patient was randomized into the ketorolac 15 mg group and the number 30 would reflect both the block to which the patient was randomized and confirm that the patient is indeed in the 15 mg group. Using both "15" or "60" and the randomization block number acts as a checks and balance to ensure that the patient is randomized into the correct group, and that the subject receives the correct randomized dose. Based on the randomization block number it is possible to know into which group the subject was randomized, the dose of ketorolac which will be administered and the order of the patient in the overall randomization. Following randomization, Subject Study Packets will be prepared.

Subject Study Packets will be prepared prior to the data collection (prior to the screening process). These packets will be created using manila envelopes capable of containing all study documents and which can be sealed. The contents of the envelopes will include the (1.) Ketorolac Research Form, (2.) Informed Consent Form (which includes consent for a POC UHCG), (3.) HIPAA Authorization Form, (4.) pretreatment VAS form, and two post-treatment VAS forms. None of the documents utilized or created throughout the study will be entered in to the subjects EHR. The manila packet and all documents contained within it will be annotated with the Subject Study Number (as described above). A description of these forms is listed below.

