#### Medication Administration

The primary investigator (PI) will maintain a resident-status through the Army-Baylor Doctor of Science Physician Assistant Studies Program for the entire research period of this study. The PI is a licensed physician assistant-certified and can under normal circumstances prescribe medication without approval by an attending physician. However due to the PI resident-status, all final treatment decisions (to include the ketorolac dosing used for this study) must be approved by a WBAMC ED attending provider.

For purposes of this study, the attending provider is usually a physician, but may be a physician assistant or nurse practitioner, and is the provider responsible for the subject's medical care at the time of data collection. Therefore, the attending provider is not a single individual. The PI may have a different attending provider for each shift or the attending may vary (being more than one individual) within one specific ED shift. Again, the attending provider is the final medical authority for every subject and it is the attending provider who will ultimately approve or disapprove ketorolac dosing regimens as they pertain to this study.

For instance, the PI may enroll and randomize a patient to the 15 mg ketorolac group. The PI will communicate this to the attending provider. However, the attending provider may reject the 15 mg dose and opt for a lower dose, higher dose or no ketorolac dose at all. For this reason, the inclusion and exclusion criteria for this study will document attending provider approval of the dosing regimen to which the patient is randomized prior to administration of the ketorolac.

The Regional Health Command Central (RHC-C) Human Research Protection Program was consulted on this issue specifically. Their guidance was that, for the purposes of this study, the attending physicians are not human subjects research in this study and do not require formal written consent to signify approval of the randomized ketorolac dose. However, they recommended that the PI obtain concurrence with the dose from the attending provider. The investigators for this study will have the attending provider sign the Ketorolac Research Form signifying their concurrence with the randomized dose.

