#### Secondary Outcome Variable Data.

The secondary outcome variables will be the number of subjects experiencing adverse events (both objective and subjective). This data will be provided by the subjects or observed, measured or verified by the investigators and will be documented on the adverse events section of the Ketorolac Research Form. Adverse events will be documented as objective and subjective adverse events. Subjects will be provided a list of the most common adverse events based on the medical website UpToDate.com. This list will be included on the Ketorolac Research Form. Subjects will be advised to circle any of the adverse events that they are experiencing. Each circled adverse event will count as 1 in a binary numbering system (1 indicating an adverse event and 0 indicating no adverse event) for purposes of analysis. Subjects may have more than one adverse event and each event will count as 1 point. The definitions of objective and subjective adverse event are provided below.

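### Self-reported adverse events pass through an investigator agreement step with the dose visible, and no rule says that the subject's circled list governs

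*Protocol*

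**What the plan says.** Four parts of the plan bear on this.

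- **Counting.** Protocol 10.2 (Secondary Outcome Variable Data) makes the outcome the number of subjects with adverse events. Subjects circle what they experience on the Ketorolac Research Form, and "Each circled adverse event will count as 1 in a binary numbering system". The form's description in section 10.1 gives the same rule.
- **Review before analysis.** Under Subjective adverse events, section 10.2 adds: "Study investigators will review, confer, agree upon and categorize the adverse events". The step rests on what the subject reported and comes before the statistician receives the data. The same paragraph defines these events as symptoms that the investigator cannot measure, see or confirm.
- **Dose visibility.** Section 9.4 reads "This study utilizes a single-blinded, randomized controlled non-inferiority trial design", without saying who is blinded. The Subject Study Number contains 15 or 60. Under Randomization and Study Subject Packet Creation, "The manila packet and all documents contained within it will be annotated with the Subject Study Number", and "Based on the randomization block number it is possible to know into which group the subject was randomized". In the Medication Administration example of a randomized 15 mg dose, "The PI will communicate this to the attending provider". The transcribed worksheet keeps the same number as its only identifier.
- **Expectation and test.** Section 9.6 says "We anticipate that there will be a lower rate of adverse outcomes by utilizing lower doses of ketorolac", and section 14.4 repeats it. Section 11.6 tests for fewer adverse effects on the lower dose with a one-sided z-test for two proportions at 0.05. The SAP names Fisher's exact test for a difference and gives no direction.

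**The concern.** The people who confer on the subject's symptoms can read the dose from the form in front of them, have stated which arm they expect to do better, and by definition hold no independent evidence on whether the symptom occurred. The plan does not say what happens when they fail to agree, or which list is analysed if the agreed one and the circled one differ.

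The treatment of the VAS in section 10.2 makes the gap more noticeable. There, measurement is put off until all data are in, expressly to limit bias, and a measurement that investigators cannot agree on is not used and the patient is excluded. So in this protocol, failure to agree already costs data in one place. For adverse events the same idea of agreement appears with neither a stated consequence nor a stated protection.

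At stake is the secondary claim that the lower dose causes fewer adverse effects, on which the benefits in sections 9.6 and 14.4 rest. If affected 15 mg subjects lost their events at this step more often than 60 mg subjects did, the comparison would tilt in the expected direction.

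**Working it through.** **The plan's own figures.** The plan gives no event rate, power or sample size for adverse events. Its only powered figure is for the VAS, with margin 13 mm, SD 27 mm, one-sided alpha 0.05 and 80% power. The normal approximation gives n = 2 × (1.645 + 0.842)² × 27² / 13² ≈ 53.3, so 54 per arm. The exact noncentral t gives 79.98% power at 54 and 80.6% at 55, so the stated 55 reproduces. Nothing below depends on it, apart from the enrolled 61 per arm (sections 11.4 and 11.5).

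**Inputs.**
- From the documents: 61 per arm; alpha 0.05; one-sided pooled z-test (Protocol 11.6); Fisher's exact test, direction not given (SAP).
- Assumed, because the documents give neither: a true share p of subjects with any event, equal in both arms; and a share r of affected 15 mg subjects, with none on 60 mg, who lose all their events at review.

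**Model.** The 15 mg count is Binomial(61, p(1 − r)) and the 60 mg count is Binomial(61, p). The false-claim rate is the total probability of all pairs of counts for which the test rejects in favour of 15 mg, found by exact enumeration.

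At p = 0.30, about 0.30 × 61 = 18.3 subjects per arm are affected. Then r = 0.10 means about 1.8 subjects lost and an apparent rate of 0.30 × 0.9 = 0.27. With r = 0.20, about 3.7 are lost and the apparent rate is 0.24.

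| Test, p = 0.30 | r = 0 | r = 0.10 | r = 0.20 |
|---|---|---|---|
| One-sided z (Protocol) | 5.1% | 10.3% | 18.9% |
| One-sided Fisher | 3.3% | 6.9% | 13.4% |
| Two-sided Fisher, 15 mg direction | 1.6% | 3.7% | 7.9% |

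**Sensitivity to the event rate.** With r = 0.20 and p from 0.10 to 0.50, the rate runs from 10.7% to 28.7% for the z-test, 6.1% to 23.2% for one-sided Fisher, and 2.6% to 16.2% for two-sided Fisher.

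**In counts.** Start from 18 affected subjects in each arm.
- Removing 8 on 15 mg leaves 10 v 18. The pooled share is 28/122 = 0.2295 and SE = √(0.2295 × 0.7705 × 2/61) = 0.0761. Then z = −(8/61)/0.0761 = −1.72 and one-sided p ≈ 0.043.
- Removing 7 leaves 11 v 18, with z = −1.49 and p ≈ 0.068.

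So 8 removals produce significance with the z-test; one-sided Fisher needs 9 and two-sided Fisher 10. Starting from 12 per arm, the z-test needs 7.

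**What the step can and cannot change.** Renaming or merging a subject's terms leaves the any-event count as it was. Only the loss of every event for a subject changes it, and a subject who also has an objective event stays counted, because the agreement step is written only for subjective events.

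**The case against.** The strongest reply is that the step only labels. The sentence ties the review to the subject's report, and sections 10.1 and 10.2 both say that each circled event counts. There is real labelling to do: objective events include reported symptoms that an investigator can observe, so someone must assign the class, and the examples of subjective events are said not to be exhaustive, so an unlisted symptom needs a category. The circled forms are also kept (at least three years in section 10.1; other sections say two), so any removal could be found later.

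Most of this stands. A reader might infer that the Protocol lets investigators delete reported events, or that it holds two conflicting counting rules. The documents do not support either: no deletion is ordered or allowed, and the two paragraphs can be read as counting and labelling. A reader might also take the one-sided z-test as settled, but the SAP names Fisher's test with no direction, and under it the effect is smaller.

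What the reply does not supply is a rule that the circled list governs if the agreed list differs, or any masking of the dose during review. Retained forms allow a check afterwards but do not decide which list the statistician analyses.

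**Conclusion.** The concern holds as an unguarded step, not as evidence of editing. Unverifiable self-reports are agreed by investigators who can read the dose, before analysis, and no rule fixes which list prevails. That leaves the secondary comparison open to bias towards 15 mg.

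The size is illustrative. It rests on an assumed event rate equal in both arms and on complete loss of events for some affected 15 mg subjects and no 60 mg subjects. At a 30% rate with 1 in 5 affected 15 mg subjects lost, false claims reach 18.9%, 13.4% or 7.9%, depending on which test and direction are finally used. With nothing lost they stay at 5.1%, 3.3% or 1.6%. The VAS analysis is not affected. The endpoint is secondary, but the protection is nearly free and worth adding.

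**What to change.** In section 10.2, Subjective adverse events:

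1. Delete *agree upon*. State that every event the subject circles or reports enters the subject-level analysis as reported, under the counting rule in Secondary Outcome Variable Data.
2. State that investigator review may only label an event, either as objective or subjective or with a category for an unlisted symptom, and may never remove one.
3. Have the labelling done from a listing in which the statistician has replaced the dose-bearing Subject Study Number with an arbitrary identifier.

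Separately, reconcile the Protocol and SAP on the test and its direction, since the size of any bias depends on both.

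The cost is a short text change and one recoded listing from the statistician already on the study. If a list has already been agreed, the count can be rebuilt from the circled entries on the retained forms. The change does not address the recording of objective events by investigators who know the dose.

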**Descriptive Statistics Data.**

Descriptive statistics data will be gathered to find correlation between subject demographics (age and gender) and location and duration of pain. These data will be obtained on the Ketorolac Research Form which is completed by the subject and will be included as descriptive statistics only. The data may or may not be analyzed for statistical significance, this will be at the discretion of the statistician. Furthermore, data pertaining to subjects requiring analgesia beyond the ketorolac used for this study, will also be collected for descriptive purposes only. Furthermore, data pertaining to subjects requiring analgesia beyond ketorolac, will be collected for descriptive purposes only. The data will be collected on the Ketorolac Data Collection Workbook, along with the other data.

At the completion of the entire data collection period for the entire study, VAS measurements will be obtained based on the methodology above and all data pertaining to the primary outcome (VAS scores), secondary outcome (adverse events) and descriptive statistics (from the Ketorolac Research Form) will be transcribed on to a Microsoft Excel work sheet. Any PHI or PII at this point will be de-identified and only the Subject Study Number will be used for identification. All paper documents will be secured in a manner previously described. The Excel worksheet is located on the PIs government issued common-access-card protected laptop. Access to this laptop requires both a common-access-card and a personal identification number (PIN) assigned to that specific common-access-card. The worksheet will therefore be highly secure and saved to the hard drive of the PIs laptop. The hard drive on the computer can only be accessed by the PI (as previously discussed) and network system administrators with permission. The AI for this research may also have a copy of the de-identified data, however, the data will be stored and secured in the exact same manner as the PI (common-access-card and PIN protected). All measures will be taken to protect the information of the study, however no PHI or PII will be stored on the Microsoft Excel work sheet.

**10.3 At any point in the study, will you request, use, or access health information in any form, including verbal, hard copy and electronic?**

Yes  No

**10.4 Review the definitions below and respond to the following two questions. If you are not sure of the answers, email [contact] for assistance.**

**The Military Health System (MHS) is defined as all DoD health plans and DoD health care providers that are organized under the management authority of, or in the case of covered individual providers, assigned to or employed by, the Defense Health Agency (DHA), the Army, the Navy, or the Air Force**

**MHS workforce members** are employees, volunteers, trainees, and other persons whose conduct, in the performance of work for the MHS, is under the direct control of the MHS, whether or not they are paid by the MHS.

**MHS business associates** are persons or entities that provide a service to the MHS and require protected health information (PHI) to provide the service.

**Are you an MHS workforce member?**

Yes, I am an MHS workforce member  
 No, I am not an MHS workforce member

**Are you an MHS business associate?**

Yes, I am an MHS business associate  
 No, I am not an MHS business associate

**10.5 Have you consulted with an MHS data expert to determine the data elements required for your study?**

Consulting with a data expert often saves time later in the compliance process because the data expert can advise on the data available in the numerous MHS information systems, the quality of that data and the methods for encrypting and collapsing data. To schedule a consult with an MHS data expert, send an email to: **([contact])**

- Yes, then complete the questions below according to the data consult
- No, then complete the questions below according to the best of your knowledge

#### **10.6 Indicate how you will request data from the MHS. Select all that apply.**

- Talking with MHS health care providers or MHS health plans about specific research participants
- Obtaining MHS hard copy records specific to research participants
- Obtaining data from an MHS information system(s)

#### **10.7 If you are obtaining data from an MHS information system(s), indicate whether you plan to receive a data extract or whether you plan to access an MHS information system directly to create a data set.**

A data extract is when the MHS or a contractor provides the data set directly to the researcher. When receiving a data set through data extract, the researcher may indicate whether the data elements should be provided as is, encrypted or collapsed. In contrast to a data extract, access to an information system means that the researcher may directly access an MHS information system and create a data set for the research study

- Data Extract
- Access

#### **10.8 Do you intend to request de-identified data from the MHS in your research study?**

There are different two methods for de-identifying data pursuant to HIPAA:

- 1) Safe Harbor Method: Removing all of the identifiers listed in Table 1 below, provided that the researcher does not have actual knowledge that the remaining data can be used alone or in combination with other information to identify the individual who is the subject of the information
- 2) Statistical Method: An expert, with appropriate knowledge of and experience with generally accepted statistical and scientific principles and methods for rendering information not individually identifiable, determines that the data is not individually identifiable

- Yes
- No

